3.1.1 Administrative structure of the trial

This study is sponsored by Boehringer Ingelheim. A Coordinating Investigator as specified on the cover page of this protocol will be nominated and will be responsible to coordinate investigators at different centres participating in this multicentre trial. Tasks and responsibilities for the Coordinating Investigator will be defined in a contract. Documents on participating (Principal) Investigators and other important participants, especially their curricula vitae, will be filed in Boehringer Ingelheim Regulatory Documents for Submission (BIRDS). Details on handling of the trial supplies including responsible institutions are given in [Section 4](#) of this protocol. The target group of Principal Investigators will be haemato-oncologists experienced and specialized in the treatment of MM and in the conduct of phase I trials. The Principal Investigator (PI) at each site will be responsible for assuring the proper conduct of the trial, patient care, and safety at the site. The investigator or in some cases one or more sub-investigators will be responsible for the daily conduct of the trial, patient visits, eCRF completion, and for assisting the CRAs in site monitoring.

Site personnel authorized by the Investigator must enter the information required by the protocol into the eCRF. A Study Monitor will visit each site in accordance with the monitoring plan and review the eCRF data against the source data for completeness and accuracy. Discrepancies between the source data and those entered onto the eCRF will be addressed by qualified site personnel. When a data discrepancy warrants a correction, that correction will be made by authorized site personnel. Data collection procedures will be discussed with the study site at the site initiation visit and/or at the Investigator's Meeting.

The study sites will use a validated electronic data capture (EDC) system to enter subjects' data from source documents onto electronic eCRFs. Password-protected access to the EDC system will be via a secure website. Data clarification forms and data corrections will be handled through the same system. All transactions within the EDC system must be fully documented within an electronic audit trail. Each set of completed eCRFs must be reviewed and electronically signed and dated by the Investigator. In compliance with remote data retention requirements, the study sites will be provided with a CD-ROM containing the eCRFs and the complete audit trail in PDF format, subsequent to database lock.

A complete list of investigators and other persons whose participation materially will affect the conduct of the trial will be filed in BIRDS and provided in the Clinical Trial Report (CTR).

The study may be outsourced for responsibilities that include site monitoring, study medication logistics and processing of safety reports, among others.

Boehringer Ingelheim has appointed a Trial Clinical Monitor (TCM), responsible for coordinating all required activities to

- Manage the trial in accordance with applicable regulations and internal SOPs,
- Direct the clinical trial team in the preparation, conduct and reporting of the trial,
- Order the materials as needed for the trial
- Ensure appropriate training and information of local monitors (CML), Clinical Research Associates (CRAs) and Investigators of participating countries.

Proprietary confidential information.

© 2018 Boehringer Ingelheim International GmbH or one or more of its affiliated companies. All rights reserved.

This document may not - in full or in part - be passed on, reproduced, published or otherwise used without prior written permission.

The safety laboratory investigations (haematological, biochemical, coagulation, and urine) and specific biomarkers ([Section 5.1.2](#), [5.2.4](#) and [5.3.3](#)) will be performed at the investigator site and no central laboratory will be used for these parameters. Only standard laboratory investigations are required by the protocol for safety laboratory investigations. The certification and/or accreditation for each laboratory or evidence that it participates in an established quality program must be provided by the investigator and filed at the Sponsor and the local ISF of the site, as well as the normal ranges of each test performed.

All trial relevant documentation will be stored in BIRDS. Trial relevant documentation which has to be at the trial site will be filed in the ISF at the investigator site. The ISF document will be kept in print-out version at the sites as far as required by local regulation and BI-SOP.

A safety committee (SC) of the investigators in cooperation with the responsible trial monitor and the medical project leader of the sponsor as well as medical representatives from Amgen will be implemented to analyse ongoing safety information and decide on further steps in dose finding. Prior to escalating the dose to the next higher dose cohort there will be a safety teleconference or meeting between trial investigators and the medical project leader of the sponsor to discuss any findings in the ongoing and already recruited cohorts, this means that all available clinical and safety data including repeated cycles of prior dose cohorts will be taken into consideration for assessments and decision making. Participation of the coordinating investigator or [REDACTED] deputy is a mandatory requirement for this committee to establish a quorum. After the defined observation period of each cohort this safety committee will discuss the need to enter additional patients or dose cohorts or release the next dose cohort and dose increment as per protocol. The same is true for the decision to switch from single patient cohorts to the 3+3 design. Step dosing may be implemented based on cytokine release syndrome qualifying for DLT following the following guidance:

- Restart with previous dose level for 4 days (one bag) and then escalate to current dose level until the end of the cycle.

The composition of the SC will be documented in BIRDS. The tasks and responsibilities will be agreed in contracts between the SC members and the Sponsor. SC will decide on the switch from single patient cohorts to the 3+3 design independently from defined dose cohorts based on clinical activity (antitumor response) and/or clinically relevant safety or pharmacodynamics findings.

Data Management and Statistical Evaluation will be done by BI according to BI SOPs.

Tasks and functions assigned in order to organise, manage, and evaluate the trial will be defined according to BI SOPs. A list of responsible persons and relevant local information can be found in the ISF.

Summary of assessments (see corresponding [Flow charts](#)):

Proprietary confidential information.

© 2018 Boehringer Ingelheim International GmbH or one or more of its affiliated companies. All rights reserved.

This document may not - in full or in part - be passed on, reproduced, published or otherwise used without prior written permission.

At screening, blood samples are drawn, a physical examination and a routine MRI scan are performed, and the patient is evaluated for eligibility in the trial. Bone marrow aspirate/biopsy will be performed. In case karyotyping of bone marrow aspirate/biopsy has been performed after the latest therapy within 3 months before start of trial medication, it should be recorded.

Clinical disease status will be assessed at screening and at the start of each new cycle (e.g. before cycle 2, 3, 4 and 5 etc.) as well as at EOT with physical examination and clinical assessment of the multiple myeloma. MRI scans in this trial will be performed prior to treatment, at screening and every other cycle at day 1, cycle 3, day 1, cycle 5, day 1, cycle 7, day 1 and/or at time of progression or start of further anticancer therapy.

Results from routine assessments (MRI) for multiple myeloma are accepted for screening if performed no later than 28 days before start of treatment.

Bone marrow examination, MRI scan and additional CT scans will be performed at time points outlined in the [Flow chart](#). Results of MRI scans, additional CT scans, optional PET scan or bone marrow examination performed during the conduct of the trial should be reported in the eCRF. After the EOT visit which must occur immediately at time of permanent discontinuation of study medication but no later than 7 days after last drug administration, the patient will have a follow up visit within 30 days after EOT (REP visit) for assessment of AEs /SAEs, patient status and further anti-cancer treatment. In case of ongoing clinical benefit, patients can be followed up to collect data for duration of response. Follow-up visits for responders will be at 3, 6 and 12 months after EOT if a patient did not progress, started a new anti-cancer treatment, died, or withdrew informed consent and will assess related SAEs and AESIs.

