4.1.4.3 Dose reductions and dose delays

Related SAEs/AEs of \geq grade 2 or non-drug related SAEs/AEs of \geq grade 2 deemed intolerable by the patient or the treating physician and not responding to appropriate medical management will result in a pause until resolution to baseline or grade 1. A pause of a maximum duration of 14 days and a dose reduction to the next lower dose level is allowed if clinically indicated. Only one dose de-escalation step is allowed.

DLT events in any cycle, cases meeting the pre-defined hepatic injury criteria (ref. [5.2.2.1](#)) and infusion related reactions or cytokine release syndromes \geq grade 3 will lead to permanent discontinuation in the dose escalation phases. After recovery to baseline or grade 1 continuation of the cycle at the next lower dose tier is allowed. Only one dose de-escalation step is allowed.

CNS events \geq grade 2 irrespective of relatedness that have not resolved to baseline or grade 1 within one week despite treatment interruption will lead to permanent discontinuation in the dose escalation phase. CNS events that have resolved to baseline or grade 1 within one week can be continued at the next lower dose level. Only one dose de-escalation step is allowed.

In case of dose reductions all future courses will also be at the reduced dose level.

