4.1.4.5 Temporary treatment interruption of BI 863909

If a pause of treatment < 14 days occurs within a cycle then the cycle will be restarted at the same or the next lower dose (if clinically indicated) and continued until the pre-scheduled end of the cycle. This dose will be continued in subsequent cycles.

If a pause of treatment occurs and less than 7 days of treatment would remain after restart of the cycle there is an option to skip the last treatment days and continue with the next course as scheduled. However, treatment should not be given for less than 14 days per cycle.

Patients who permanently discontinue treatment for reasons other than DLT will be replaced. Only patients who will receive at least 14 days of treatment in the first course will be evaluable for the primary analysis unless they develop DLT.

For dose levels 2 and higher the trial safety committee may decide to start the subsequent cycles of the affected patient and potentially new patients at this and higher dose cohorts in a stepwise fashion: treatment will be started at 10-30% of the target dose for the first week (but not earlier than 4 days after the stop of infusion in retreated patients). On day 9 the dose may be escalated to the target dose.

The re-start of the infusion should be performed in the hospital under supervision of the investigator.

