5.2.1.1 Dose limiting toxicity

Dose limiting toxicity (DLT) is defined as any drug-related non-haematological adverse event CTCAE version 4.03 grade 3 or higher. The following grade 3 events will not be considered

Proprietary confidential information.

© 2018 Boehringer Ingelheim International GmbH or one or more of its affiliated companies. All rights reserved.

This document may not - in full or in part - be passed on, reproduced, published or otherwise used without prior written permission.

DLT: febrile neutropenia and infection responding to antibiotic/anti-infective treatment within 48 hours, fatigue, headache, insomnia, fever, hypotension.

Laboratory parameters of grade ≥ 3 but not considered clinically relevant and/or responding to routine medical management, will not be considered dose limiting toxicities.

Additional events that are considered DLT include:

- Persistent grade 4 neutropenia or thrombocytopenia until day 56 in the absence of detectable Multiple Myeloma as it may reflect a marrow toxic effect of BI 836909.

If infusion related reactions (IRR) or cytokine release syndromes (CRS) \geq grade 2 occur or constitute DLT events the safety committee may decide to switch to step dosing for the respective and any higher dose cohort. In that case the infusion will be started at 10(-30)% of the target dose on day 1 of the course and will be escalated to the full target dose from day 9 of course 1 on for the remainder of the course. Patients will be hospitalized and pre-medicated for the dose increase the same way they are for start of treatment. Once the safety committee decides to switch to step dosing patients that may have developed DLT due to IRR or CRS events may be replaced at the respective cohort by additional patients who will receive treatment with the adapted administration schedule (step dosing).

Although hematological adverse events (e.g. anemia, thrombocytopenia, neutropenia, lymphopenia) will not be considered DLT, complications resulting from hematological events, e.g. bleeding due to thrombocytopenia or grade 4 infection due to neutropenia are classified as non-hematological adverse events and are covered by the above definition of DLT. Nevertheless, hematological adverse events will be considered for definition of the dose for further development.

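### Section 3.1.1's step-dosing rule for CRS that counts as a DLT has no stated scope: as a cohort schedule it contradicts 5.2.1.1, and as a restart rule it contradicts 4.1.4.3

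*Protocol*

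**What the plan says.** - **Protocol 3.1.1** gives the safety committee this option: "Step dosing may be implemented based on cytokine release syndrome qualifying for DLT". The schedule is one bullet: "Restart with previous dose level for 4 days (one bag) and then escalate to current dose level until the end of the cycle". It names no patient group and no cycle, and refers to no other section.
- **Protocol 5.2.1.1** applies when CRS or infusion-related reactions (IRR) reach grade 2 or constitute DLTs, so it includes the 3.1.1 trigger. The committee may switch the affected cohort and any higher one. Then "the infusion will be started at 10(-30)% of the target dose on day 1 of the course" and the dose "will be escalated to the full target dose from day 9 of course 1 on for the remainder of the course". After the switch, "patients that may have developed DLT due to IRR or CRS events may be replaced at the respective cohort" by step-dosed patients.
- **Protocol 4.1.4.3** first says that a DLT in any cycle, or CRS or IRR of grade 3 or higher, ends treatment permanently. It continues: "After recovery to baseline or grade 1 continuation of the cycle at the next lower dose tier is allowed". Only one step down is permitted, and "In case of dose reductions all future courses will also be at the reduced dose level".
- **Protocol 4.1.4.5** lets the committee, from dose level 2 upward, "start the subsequent cycles of the affected patient and potentially new patients at this and higher dose cohorts in a stepwise fashion": 10-30% of target at first, with an optional increase to target on day 9.
- **Protocol 4.1.4.1.4** rules out re-exposure after IRR of grade 3 or 4. Its CRS table permits a restart after grade 3 on the grade 2 terms, which set no dose for a first event, and stops treatment for good at grade 4.
- **SAP 6.1 and 6.3** label dose groups by µg/d only and leave replaced patients out of the MTD evaluation set (MTDS), on which the primary DLT analysis rests.

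**The concern.** The same committee, facing the same event, finds two step-dosing schedules and nothing that ranks them or assigns them to different patients. In both sections the discretion is over whether to step-dose; once that is decided, each section prescribes its own schedule.

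Two things are at stake. One is the run-in dose of a step-dosed cohort in a trial whose staggered entry is there to watch for early cytokine release. The other is whether a patient who has had a grade 3 CRS DLT may go back to the dose that caused it. The primary endpoint is touched as well: step-dosed patients can replace patients with a CRS DLT at the same nominal dose, and the visible SAP labels do not show which schedule a patient received.

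**Working it through.** The documents give no figure of their own for this point, so the check is a comparison of the rules plus arithmetic on the dose ladder in Protocol Table 3.1: 1.

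**Reading A: 3.1.1 as a cohort schedule, compared with 5.2.1.1.** First step under 3.1.1 = previous level. First step under 5.2.1.1 = 0.10 to 0.30 × current level.

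| Current level (µg/day) | 3.1.1 first step | Previous/current | 5.2.1.1 first step |
|---|---|---|---|
| 3.2 | 1.6 | 0.50 | 0.32-0.96 |
| 6.5 | 3.2 | 0.492 | 0.65-1.95 |
| 13 | 6.5 | 0.50 | 1.3-3.9 |
| 25 | 13 | 0.52 | 2.5-7.5 |
| 50 | 25 | 0.50 | 5-15 |
| 100 | 50 | 0.50 | 10-30 |
| 200 | 100 | 0.50 | 20-60 |
| 400 | 200 | 0.50 | 40-120 |
| 800 | 400 | 0.50 | 80-240 |

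- Smallest ratio of first steps: 0.492/0.30 = 1.6. Largest: 0.52/0.10 = 5.2. At 400 µg/day: 200/120 = 1.7 to 200/40 = 5.0.
- Intermediate cohorts, assuming that the previous level means the next lower one: 50/75 = 100/150 = 200/300 = 400/600 = 0.67. The ratio is then 0.667/0.30 = 2.2 to 0.667/0.10 = 6.7.
- Full dose is reached on day 5 (after 4 days) against day 9.

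The previous level is never as low as 30% of the current one, so the two schedules cannot be the same regimen at any level.

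**Reading B: 3.1.1 as a restart of the affected patient, compared with 4.1.4.3.**

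- If the first sentence of 4.1.4.3 governs, no further dose is permitted, and every day of the 3.1.1 schedule breaks the rule.
- If the second sentence governs, the first 4 days comply, because the previous level is the next lower tier. The return to the current level does not. It gives 1/0.52 = 1.9 to 1/0.492 = 2.0 times the permitted tier (1/0.667 = 1.5 for intermediate cohorts); for example, 400 against 200 µg/day.

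**Section 4.1.4.5 by type of event.**

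| Event in the affected patient | What the other rules allow | Stepping back to the original target |
|---|---|---|
| Grade 2 CRS, not a DLT | CRS table: restart; 4.1.4.3: reduction optional | No conflict |
| Grade 3 CRS, a DLT | CRS table: restart, dose not stated; 4.1.4.3: discontinue, then next lower tier | Conflict |
| Grade 4 CRS | CRS table: discontinue | Conflict |
| Grade 3 or 4 IRR | 4.1.4.1.4: no re-exposure | Conflict |

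In the grade 3 CRS case, an uninterrupted 28-day infusion stepped up on day 9 has 28 − 8 = 20 days at target; for example, at 400 where the second sentence of 4.1.4.3 permits 200 µg/day.

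**The case against.** The strongest reply is that the sections can be kept apart. The 3.1.1 bullet speaks of a restart and of the end of the cycle, 5.2.1.1 sets how a course begins for a cohort, and 4.1.4.5 deals with later cycles. On that view 3.1.1 and 5.2.1.1 never compete, and a first-step ratio would compare a restart after recovery with an initial dose. This is plausible, and it limits the point: the two conflicts belong to alternative readings. A reader might infer that both hold at once; the text does not support that. But the separation is nowhere stated, and the reading that removes the first conflict creates the second.

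A reader might also infer that 4.1.4.5 always contradicts 4.1.4.3. It does not. Its stepwise paragraph names no DLT trigger, and after a grade 2 interruption a reduction is optional.

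There are safeguards. A restart under the CRS table requires prior consultation with the sponsor's medical monitor, and the sponsor confirms each new patient's dose in writing. These make an unconsidered choice less likely but do not tell the monitor or sponsor which rule applies.

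Finally, a reader might infer that DLTs are lost or the MTD is biased. The documents do not support that. DLTs of replaced patients remain in the Treated Set tables (SAP 7.8), infusion-rate changes are recorded in the eCRF, and mixed run-ins within a cohort are possible, not certain. The labelling gap arises from 5.2.1.1 alone, and parts of the SAP are not visible.

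**Conclusion.** The point holds, and the text should be corrected. The 3.1.1 bullet lacks a scope, and neither available reading is consistent with the rest of the protocol. As a cohort schedule, its first step is 1.6 to 5.2 times that of 5.2.1.1 on the ladder from 3.2 µg/day (2.2 to 6.7 times for intermediate cohorts). As a restart, it returns the patient to 1.5 to 2.0 times the highest dose that 4.1.4.3 could allow. Section 4.1.4.3 adds to the problem by contradicting itself. Section 4.1.4.5 conflicts only for a patient with a DLT or with CRS or IRR of grade 3 or higher.

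The figures assume that the previous level is the next lower one, and the 20-day figure assumes an uninterrupted infusion. The effect on the MTD cannot be quantified from the documents, and none is claimed.

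**What to change.** 1. **Protocol 3.1.1 and 5.2.1.1.** Make 5.2.1.1 the step-dosing schedule for new and replacement patients, and replace the 3.1.1 bullet with a cross-reference to it.
2. **Protocol 4.1.4.3.** Remove the internal contradiction. State that a patient with a grade 3 CRS DLT who may restart under the CRS table continues only at the next lower tier, and that all others with a DLT or grade 4 CRS discontinue. Align 4.1.4.3 and the IRR guidance in 4.1.4.1.4 with each other.
3. **Protocol 4.1.4.5.** Limit stepping back to the original target to affected patients without a DLT and without CRS or IRR of grade 3 or higher. For any other patient who may continue, the target is the reduced tier.
4. **SAP.** Flag step-dosed patients in the cycle 1 DLT tables, on both the MTDS and the Treated Set, and report the dosing schedule together with the MTD or recommended dose.

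The cost is protocol wording and one table flag. No new procedure, sample or patient is needed.

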| Body temperature | X | X | X | X | X | X | | X | X | X | X | X | | X | X | X | X | X | X | |
| Blood pressure (with heart rate) | X | X | X | X | X | X | | X | X | X | X | X | | X | X | X | X | X | X | |
| 12-lead ECG (local) ¹¹ | X | | | | | | | X | | | | | | X | | | | | | X |
| General safety laboratory parameters ¹² | X | X | X | X | X | X | X | X | X | X | X | X | X | X | X | X | X | X | X | |
| Screening for HCV, HBV, HIV | X | | | | | | | | | | | | | | | | | | | |
| Serum pregnancy test | X | | | | | | | X | | | | | | X | | | | | | X |
| Hospitalisation ⁷ | | X | | | | X ⁷ | | X | | | | | | X | | | | | | |
| Home Care Support ¹³ | | | X | X | X | X | X | X | X | X | X | X | X | X | X | X | X | X | | |
| Concomitant therapy | X | X | X | X | X | X | X | X | X | X | X | X | X | X | X | X | X | X | X | |
| Adverse events | | X | X | X | X | X | X | X | X | X | X | X | X | X | X | X | X | X | X | X |
| Eligibility for treatment | | X | | | | | | X | | | | | | X | | | | | | |
| Administration of BI 836909 | | X | c.i.v. | | | X | | X | c.i.v. | | | X | | X | c.i.v. | | | X | | |
| Disease / response assessment (clinical/MRI) ¹⁴ | X | | | | | | | X | | | | | | X | | | | | X | |
| Pharmacokinetics ¹⁵ | | see separate flow chart | | | | | | | | | | | | | | | | | | |
| Reason for treatment discontinuation / IWRS call | | | | | | | | | | | | | | | | | X | | | |
| Next line of anti-cancer therapy | | | | | | | | | | | | | | | | | | X | | |
| Patient status | | | | | | | | | | | | | | | | | | X | | |

1 each course has a duration of 6 weeks, 4 weeks of continuous infusion of BI 836909 and 2 weeks break.

[figure not shown]
- 2 EOT will be performed after permanent discontinuation of trial medication or as soon as possible but no later than 1 week after discontinuation of trial drug ([Section 6.2.5.1](#))
- 3 Follow up visit should be performed 30 days after the EOT (REP visit). In case of ongoing clinical benefit, patients can be followed up to collect data for duration of response. Follow-up visits for responders will be at 3, 6 and 12 months after EOT if a patient did not progress, started a new anti-cancer treatment, died, or withdrew informed consent.
Follow up visit after EOT: report all AEs, SAEs, AESIs regardless of relatedness. This includes all deaths unless due to underlying disease ([Section 6.2.5.2](#))
Extended follow up: report related SAEs and AESIs.

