- Follow up visit (FU): follow up visit should be performed 30 days after the EOT (REP visit). Patients will be treated for a maximum of 10 cycles. In case of ongoing clinical benefit, patients can be followed up to collect data for duration of response. Follow-up visits for responders will be at 3, 6 and 12 months after EOT if a patient did not progress, started a new anti-cancer treatment, died, or withdrew informed consent. Last patient out is defined as the REPlast visit completed by the last patient. This will be the end of the trial.

For patients who have entered the trial before the approval of the second revision last visit would be defined as the last follow up visit after the approval date.

For patients who have re-consented after the approval of the fourth revision last visit would be defined as above.

The following dose levels will be tested:

Table 3.1: 1 Dose escalation scheme

| Dose level | Dose µg/d | Patients per cohort | Approximate increment to next dose |
|------------|-----------|---------------------|------------------------------------|
| 1 | 0.2 | 1 | 2x |
| 2 | 0.4 | 1 | 2x |
| 3 | 0.8 | 1 | 2x |
| 4 | 1.6 | 1 | 2x |
| 5 | 3.2 | 3 (+3) | 2x |
| 6 | 6.5 | 3 (+3) | 2x |
| 7 | 13 | 3 (+3) | 2x |
| 8 | 25 | 3 (+3) | 2x |
| 9 | 50 | 3 (+3) | 2x |
| 10 | 100* | 3 (+3) | 2x |
| 11 | 200* | 3 (+3) | 2x |
| 12 | 400* | 3 (+3) | 2x |
| 13 | 800* | 3 (+3) | 2x |

*Intermediate dose cohorts with up to 50% increment versus the previous cohort will be entered if determined by the safety committee, in case that the dose of a cohort exceeds MTD (> 1 patient out of 6 with DLT) and the previous cohort is well tolerated.

For example:

Proprietary confidential information.

© 2018 Boehringer Ingelheim International GmbH or one or more of its affiliated companies. All rights reserved.

This document may not - in full or in part - be passed on, reproduced, published or otherwise used without prior written permission.

- 75µg/day in case a dose of 100µg/day exceeds MTD
- 150µg/day in case a dose of 200µg/day exceeds MTD
- 300µg/day in case a dose of 400µg/day exceeds MTD
- 600µg/day in case a dose of 800µg/day exceeds MTD

The above-mentioned intermediate dose cohorts will follow the 3 (+3) design. The starting dose will be 0.20 µg/day given as a continuous intravenous infusion for 4 weeks.

An every 6-week regimen will be tested (4 weeks of continuous intravenous administration of BI 836909 followed by a 2 weeks off-period).

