5.2.3 Adverse event collection and reporting

AE Collection

The following must be collected and documented on the appropriate eCRF by the Investigator:

- From signing the informed consent onwards through the Residual Effect period (REP) which is 30 day after EOT until the end of REP all AEs (serious and non-serious) and AESIs must be reported
- After the end of REP until trial completion all related SAEs and related AESIs must be reported.

The REP is defined as 30 days after the last administration of study medication. All AEs which occurred through the treatment phase and throughout the REP will be considered as on treatment please. Events which occurred after the REP will be considered as post treatment events.

After the last per protocol contact the Investigator does not need to actively monitor patients for AEs. However, if the Investigator becomes aware of SAEs or AESIs that occurred after the last per protocol contact, the SAEs and AESIs should be reported by the Investigator to the Sponsor if considered relevant by the investigator.

Patients may be hospitalized during selected phases of the study as required per protocol, e.g., monitoring of trial drug administration, collection of blood for pharmacokinetic purposes, or for administrative reasons. Hospitalizations for administrative reasons and other hospitalizations already planned at the screening visit need not be reported as a SAE in case they are performed "as planned".

Proprietary confidential information.

© 2018 Boehringer Ingelheim International GmbH or one or more of its affiliated companies. All rights reserved.

This document may not - in full or in part - be passed on, reproduced, published or otherwise used without prior written permission.

The investigator must report the following events via telephone/fax using the SAE form immediately (within 24 hours) to the sponsor: SAEs and non-serious AEs occurring at the same time as an SAE and/or which are medically related to the SAE(s), and Protocol-specified adverse event of special interest. With receipt of any further information to these events, a follow-up SAE report has to be provided. SAEs and non-serious AEs must include a causal relationship assessment made by the investigator.

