6.2.5.2 Residual effect period (REP)

The REP is defined in [Section 5.2.3](#). The End of REP (EOR) visit should not be performed earlier than 30 days after permanent discontinuation of the trial medication. The information collected at this visit should include all new AEs that occurred after EOT and a follow-up of adverse events ongoing at EOT. Any subsequent anti-cancer therapy administered between EOT and REP visit must be documented to allow an assessment of newly reported AEs as well as patient's status.

Table 6.2.5.3: 1 Residual effect period (REP)

| | |
|---|--|
| Adverse events (Section 5.2.2) | All AEs, SAEs, AESIs regardless of related ness. This includes all deaths. |
| Patient status | Collect information for progression or relapse, death, lost to follow-up. |
| Other therapy for Multiple Myeloma | In case the patient receives other therapy for Multiple Myeloma |

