Table 6.1: 2 Definition of treatment periods

Analyzing Treatment Period	Start Date	Start Time	End Date
Screening	Date of informed consent		Date of the first administration of BI 836909
Treatment	Date of the first administration of BI 836909	Time of the first administration of BI 836909	Date of the last administration of BI 836909
Residual effect period	Date of the last administration of BI 836909 + 1 day		Date of the last administration of BI 836909 + 30 day
Post-treatment	Date of the last administration of BI 836909 + 31 day		Not applicable

For safety analyses, adverse events (AEs) will be classified to one of the following time periods: “Screening”, “Treatment”, or “Post-treatment”. Section 5.2.2 of the protocol specifies that all AE reported within 30 days of the last trial medication will be considered on treatment. Detailed rule for assigning AEs to these time periods are listed below:

- If the date of informed consent \leq AE onset date $<$ date of first administration of BI 836909, then the AE is assigned to “Screening”;
- If date of first administration of BI 836909 \leq AE onset date \leq date of last administration of BI 836909 + 30 days, then the AE is assigned to “Treatment”;
- If AE onset date $>$ date of last administration of BI 836909 + 30 days, then the AE is assigned to “Post-treatment”.

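### The residual effect period has two definitions and its closing visit three timings, so active adverse event follow-up can end before the 30-day window that the SAP tabulates

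*Protocol*

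**What the plan says.** **Length of the REP.** Protocol section 5.2.3 gives it twice. All adverse events are to be collected "through the Residual Effect period (REP) which is 30 day after EOT". The next paragraph says "The REP is defined as 30 days after the last administration of study medication". Section 7.3.4 bases treatment-emergent events on the end of the REP and refers back to 5.2.3 for the definition.

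**Timing of the closing visit.** There are three rules:
- Section 3.1.1, summary of assessments: "the patient will have a follow up visit within 30 days after EOT (REP visit".
- Flow chart footnote 3: "Follow up visit should be performed 30 days after the EOT (REP visit". Section 3.1 says the same.
- Section 6.2.5.2: the visit "should not be performed earlier than 30 days after permanent discontinuation of the trial medication".

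**Timing of EOT.** Section 3.1.1 allows at most 7 days after the last administration. Section 6.2.5.1 allows one week after permanent discontinuation, but also allows EOT when the decision to stop is taken or becomes known.

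**After the REP.** Under 5.2.3, only related SAEs and related AESIs are then reportable. The same section says that active monitoring for adverse events is not needed after the last per-protocol contact.

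**SAP.** Table 6.1: 2 ends the residual effect period at "Date of the last administration of BI 836909 + 30 day". Section 7.8.1 sends later events to the post-treatment category, for listings only.

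**The concern.** The SAP treats every day up to last administration + 30 as observed time for treatment-emergent events. That is sound only if sites look for events over the whole of that time. The visit that collects new events after EOT can, under one protocol rule, take place before day 30. For a patient without extended responder follow-up it is also the last scheduled contact.

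Non-serious events late in the window could then go unrecorded, and the tables would carry no sign of it. In a small dose-escalation trial whose secondary objectives include the safety profile, completeness of these counts by dose level matters. For a patient who stops in cycle 1, the SAP's Course 1 window for DLTs (to the start of cycle 2 or 30 days after the last cycle 1 dose, whichever is earlier) can also depend on this visit.

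Sites that instead time the visit from EOT may collect events that the SAP does not tabulate.

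**Working it through.** The 30 days is a definition, not a calculated figure, so the check is date arithmetic. Let day 0 be the last administration, E the day of EOT, and v the number of days from EOT to the closing visit. The 7-day limit in section 3.1.1 gives E = 0 to 7. Permanent discontinuation in 6.2.5.2 is read as the last administration; if it means a later decision date, that visit only moves later.

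| Rule | Formula | Day after last administration | Against SAP day 30 |
|---|---|---|---|
| SAP 6.1; protocol 5.2.3, last-administration definition | 30 | 30 | same |
| Protocol 5.2.3, EOT definition of REP | E + 30 | 30 to 37 | 0 to 7 days later |
| Visit, footnote 3 and section 3.1 | E + 30 | 30 to 37 | 0 to 7 days later |
| Visit, section 3.1.1 | E to E + 30 | 0 to 37 | 30 days earlier (theoretical limit) to 7 days later |
| Visit, section 6.2.5.2 | at least 30 | 30 or later, no upper limit | never earlier |

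**1. Does the reporting duty itself stop early?** The switch to related SAEs and AESIs is tied to the end of the REP, not to the visit. The REP ends on day 30 or day E + 30. As E is at least 0, the earlier of the two is day 30. The written duty therefore never falls short of the SAP window.

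**2. Can active ascertainment stop early?** The uncovered time is 30 − (E + v) days when this is positive. The visit timings here are assumptions; the documents give none.
- E = 0, v = 10: 30 − 10 = 20 days.
- E = 0, v = 14: 30 − 14 = 16 days.
- E = 0, v = 29: 30 − 29 = 1 day.
- E = 7, v = 21: 30 − 28 = 2 days.
- No gap once v is at least 30 − E, that is, 30 days for E = 0 and 23 days for E = 7.

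**3. How far does EOT + 30 overrun?** (E + 30) − 30 = E, so 0 to 7 days. As an illustration under the alternative wording in 6.2.5.1, assume that the decision to stop is taken at the end of the 14-day break and EOT follows 0 to 7 days later. Then E = 14 to 21, EOT + 30 is day 44 to 51, and the overrun is 14 to 21 days. That E breaches the 7-day limit in 3.1.1, so the two EOT rules conflict as well.

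**4. DLTs.** Section 5.2.2.1 makes any event that qualifies as a DLT an AESI, and the general DLT definition in 5.2.1.1 requires drug-relatedness. Such events remain reportable after the REP. What an early visit can weaken is how actively they are looked for, and only in patients who stop in cycle 1.

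**The case against.** The strongest reply is that the documents already point to one answer. Section 3.1.1 is a summary that defers to the flow charts. A visit on day 10 would breach the flow chart, section 3.1 and the section that governs the visit: "The End of REP (EOR) visit should not be performed earlier than 30 days after permanent discontinuation of the trial medication". The explicit definition in 5.2.3 matches the SAP, and events collected past day 30 are still listed, so nothing is lost in that direction.

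Much of this stands. The overrun is untidy rather than harmful, and most of the text argues against an early visit. It does not remove the conflict, because 3.1.1 is current text and a site following it breaks no rule stated there.

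Three stronger readings are tempting, and the documents do not support them:
- *Sites may close full adverse event reporting before day 30, so incidences are too low.* Step 1 shows that the written duty always reaches day 30. Under-ascertainment is possible, not established.
- *A fixed share of the window is lost.* A visit at day 10 after a 28-day infusion would leave 20 of 58 days (34%), but day 10 appears nowhere in the documents.
- *DLTs are lost from the primary analysis.* They are AESIs and stay reportable when related.

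**Conclusion.** The inconsistency is real and in current text. The REP has two definitions that agree only if EOT falls on the day of the last dose. The closing visit has three timings that cannot all serve as the rule.

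The consequence is limited to ascertainment. A visit that complies with 3.1.1 may end active follow-up before the SAP window closes, so non-serious events late in the window may be missed. The 20 to 1 uncovered days rest on EOT falling on the last-dose day, a visit at EOT + 10 to EOT + 29, and no responder follow-up. How many patients would be affected cannot be judged from the documents.

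The overrun is 0 to 7 days, and 14 days or more only under the alternative EOT wording in 6.2.5.1. The DLT escalation rule and the SAP cut-off are unaffected. This does not threaten the design, but it bears on how complete the safety tables are and should be corrected.

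**What to change.** Use last administration as the single anchor, as the SAP and one of the two definitions in 5.2.3 already do.

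- In sections 3.1.1 and 3.1 and in flow chart footnote 3, set the REP visit at no earlier than 30 days after the last administration.
- In section 6.2.5.2, use the same term, so that discontinuation cannot be read as the decision date.
- In section 5.2.3, delete the clause that equates the REP with 30 days after EOT.
- Reconcile the EOT timing in 3.1.1 and 6.2.5.1.
- In SAP section 6.1, align the start of the follow-up period, which is + 30 days in the text and + 31 days in Table 6.1: 2.

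Follow-up would then reach day 30 in every patient who attends and match the SAP window. The earliest permitted visit would be 23 to 30 days after EOT, for EOT on day 7 to day 0. No new visit or data item is needed. The cost is a wording amendment, with some visits moving a few days.
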